## 7.1 Primary Endpoint

The primary efficacy objective is to evaluate the efficacy of ibrexafungerp in the treatment of severe fungal diseases by a Data Review Committee (DRC) at the primary timepoint for the fungal disease (as defined in [Table 5](#)). The primary efficacy endpoint of the study is the percentage of subjects who achieve Global Response (as defined in [Table 6](#)) at TOC (Day 17) for VVC, CMC (EOT or Day 84), CPA (EOT or Day 90) and ABPA (EOT or Day 90) (whichever comes first) and at EOT for all other diseases, as determined by the DRC. The analysis criteria will be based on EORTC-MSG Consensus Criteria for all diseases except ABPA, CPA and VVC.

Table 6 EORTC-MSG General Criteria for Global Responses to Antifungal Therapy with adaptations a and b

Global Response	Outcome Criteria
Success	Complete Response: Survival within the prespecified period of observation, resolution of all attributable symptoms and signs of disease and radiological abnormalities, and mycological evidence of eradication of disease a For subjects who were enrolled for step-down therapy and who were asymptomatic at baseline: no new symptoms or signs suggestive of disease and no new positive cultures.
	Partial Response: Survival within a prespecified period of observation, improvement in attributable symptoms and signs of disease and radiological abnormalities, and evidence of clearance of cultures or reduction of fungal burden, and no new positive cultures, as assessed by a quantitative and validated laboratory marker
Failure	Stable Response: Survival within a prespecified period of observation and minor or no improvement in fungal disease, but no evidence of progression, as determined on the basis of a composite of clinical, radiological and mycological criteria.
	Progression of Fungal Disease: Evidence of progressive fungal disease based on a composite of clinical, radiological and mycological criteria
	Death: Death during the prespecified period of evaluation, regardless of attribution
bNot Evaluable	Outcome cannot be assessed due to missing data

aDefinition added in Amendment 3 for subjects enrolled for step-down therapy and asymptomatic at baseline. DRC adjudications followed this definition for all subjects, PI adjudication followed this definition for subjects enrolled after Amendment 3.

bCategory added for non-evaluable subjects due to missing data

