11.3 Discontinuation Criteria

A subject may be discontinued from the study or study drug for any of the following reasons:

- Withdrawal of consent by the subject and/or subject's legal guardian;
- Investigator or Sponsor decision that withdrawal is in the subject's best interest;
- Deterioration of the clinical condition or delayed response requiring, in opinion of the Investigator, alternative therapy;
- Occurrence of an AE that, in the opinion of the Investigator, warrants discontinuation of the subject from the study drug;
- Pregnancy;
- Lost to follow up (every attempt should be made to contact the subject).

The reason for a subject's discontinuation of treatment or withdrawal from the study will be clearly documented in the source documents and on the electronic case report form (eCRF).

For VVC subjects, all TOC procedures should be performed for subjects who discontinue from the study before the TOC visit, and all 25-Day FU procedures should be performed for subjects who discontinue from the study after the TOC visit but before the 25-Day FU visit.

For all other fungal diseases, at the time of discontinuation, all EOT procedures should be performed for subjects who discontinue from treatment on or before the EOT visit and the 6-Week FU visit should also be completed. All 6-Week FU procedures should be performed for subjects who discontinue from the study after the EOT visit and on or before the 6-Week FU visit. All follow up visits should be completed for discontinued subjects regardless of need for additional antifungal therapy.

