**Table 1 Summary of Overall Treatment and Follow-Up Schedule for All Subjects Except VVC Subjects**

Pre-study Activities	Ibrexafungerp Loading Dose	Ibrexafungerp Maintenance Dose	TOC	EOT	6-Week Follow-Up	Additional Follow-Ups
Screening a (Days -1 [-3])	Day 1 a (Baseline) & Day 2	Day 3 to EOT	EOT or Day 84 (CMC) EOT or Day 90 (CPA and ABPA) whichever comes first	Last dose of study drug (up to 180 days from Day 1)	6 weeks ( $\pm 7$ days) after EOT	3 and 6 months after EOT for ABPA subjects only

Abbreviations: ABPA = allergic bronchopulmonary aspergillosis; CMC = chronic mucocutaneous candidiasis; CPA = chronic pulmonary aspergillosis; EOT = end of treatment; TOC = test of cure

a: Screening and Baseline (Day 1) may occur on the same day.

Subjects with VVC will have a Screening visit, a Baseline/Day 1 visit, and scheduled visits on [REDACTED], Day 17 (TOC), 25-day FU (Day 32) and 35-day FU (Day 42). VVC subjects will receive treatment [REDACTED] [REDACTED]. The EOT and 35-Day FU visits may be a phone contact for asymptomatic subjects. A summary of the overall treatment and follow-up schedule for VVC subjects is provided in [Table 2](#).

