### **3.2 Analysis Populations**

The analysis populations to be used in the analysis are defined as follows:

**Intent-to-Treat Population:** The intent-to-treat (ITT) population will include all subjects who are enrolled in the study and receive at least 1 dose of study drug.

**Myco-ITT:** the Myco-ITT population will include all ITT subjects with confirmed pathogens and who also had all necessary cultures or mycology tests to estimate mycological response.

**Per-Protocol Population:** The per-protocol (PP) population will include all ITT subjects who received enough study drug (ibrexafungerp) to enable clinical efficacy judgement as determined by the DRC, who have an EOT (TOC for VVC, CMC, CPA and ABPA as applicable) assessment and who have no major protocol violations that could impact the assessment of efficacy (Refer to Section 7).

**Safety Population:** The safety population will include all subjects who receive at least one dose of study medication and have at least one safety assessment post Baseline.

**Pharmacokinetic Population:** The pharmacokinetic (PK) population will include all enrolled subjects who provide at least one PK sample and no deviations significant enough to affect the interpretability of PK data.

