## 7. EFFICACY

The primary efficacy and secondary efficacy endpoints will be performed on the ITT, Myco-ITT and PP populations. The ITT analyses will be considered primary and the Myco-ITT and PP analysis will be considered supportive of the primary analyses on the ITT population.

The primary efficacy endpoint of the study is the percentage of subjects who achieve Global Response at TOC for VVC (Day 17), CMC (EOT or Day 84), CPA (EOT or Day 90) and ABPA (EOT or Day 90) (whichever comes first) and at EOT for all other diseases, as determined by the DRC. The primary efficacy endpoint will also be summarized by disease category and reason for enrollment separately. Secondary efficacy endpoints include the percentage of subjects who achieve Global Response, Clinical Response and Mycological Response by pathogen, fungal disease, disease category, and reason for enrollment at several time points as assessed by the DRC and by the Investigator. The following enrollment categories, as determined by the DRC unless stated otherwise, will be utilized: Refractory, Intolerant, Resistant (includes step-down cases), Toxicities, Relapse, Step-Down (as determined by PI). Each subject's enrollment reason will be validated by the DRC. The percentage of subjects with a recurrence, ACM and time to death will also be assessed.

Efficacy outcomes will be based on definitions captured in [Table 5](#) and [Table 6](#). Criteria for the DRC assessment of response will be further detailed in the DRC Charter. Criteria for the Investigator is outlined in [Section 7.2](#).

Efficacy evaluations will consist of clinical evaluations of the signs and symptoms of infection, mycological testing (including, but not limited to, fungal culture, KOH and other fungal stains, and T2 testing), imaging (e.g., CT, MRI, X-Ray or ultrasound) and serological testing (including, among others,  $\beta$ -D-glucan levels, GM and fungal antibody titers) as applicable for each fungal disease. Additional procedures (esophagoscopy, spirometry, St. George's Respiratory Questionnaire [SGRQ], 6-Minute Walk Test and Medical Research Council [MRC] Dyspnea Scale) will be conducted for selected fungal diseases.

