### 7.1.1 Primary Analysis

The primary efficacy analysis will be performed at TOC for VVC (Day 17), CMC (EOT or Day 84), CPA (EOT or Day 90) and ABPA (EOT or Day 90) whichever comes first, and at EOT for all other diseases. For CMC, CPA, and ABPA, if Day 84 or Day 90 is the earlier visit and the Global Response is not evaluable or was not done, and the EOT visit has a Global Response, then the EOT information will be used. The number and percentage of subjects with Successful Global Response as determined by the DRC will be presented separately for each fungal disease, disease category, enrollment category, and pathogen along with a 95% confidence interval (CI) for a single binomial proportion in the ITT and PP populations. The Clopper Pearson method will be used for the confidence interval. CI will not be estimated when the subjects in a particular disease, disease category, enrollment category, or pathogen is less than 5. In addition, the overall response will be presented for all disease categories combined.

The following disease categories and fungal diseases will be used for the analysis.

- Acute invasive candidiasis (IC), including candidemia
  - Acute IC with/without candidemia
  - Candidemia only
- Chronic candidiasis
  - Chronic IC
  - Chronic mucocutaneous candidiasis (CMC)
- Mucocutaneous candidiasis
  - OPC (including oropharyngeal, laryngeal)
  - EC
  - VVC
- Disseminated /invasive dimorphic fungi
- Aspergillus syndromes
  - CPA
  - ABPA
  - IPA
- Other emerging fungi

The following pathogens will be used for the analysis.

- Invasive Candidiasis, including candidemia
  - Albicans
  - Auris
  - Glabrata
  - Krusei
  - Parapsilosis
  - Tropicalis

- Other Candida species
- Mucocutaneous Candidiasis (CMC, OPC, EC, VVC)
  - Albicans
  - Auris
  - Glabrata
  - Krusei
  - Parapsilosis
  - Tropicalis
  - Other Candida species
- Dimorphic fungi
  - Coccidioidomycosis
  - Histoplasmosis
  - Blastomycosis
  - Other Dimorphic fungi species
- Aspergillus Syndromes (CPA, ABPA, IPA)
  - Flavus
  - Fumigatus
  - Nidulans
  - Terreus
  - Other Aspergillus species

Invasive Candidiasis will be grouped according to the following sites of infection:

- Pleural/Pulmonary
- Intraabdominal / Pelvic
- Soft tissue/wound
- Endovascular/endocarditis
- Mediastinitis
- Osteomyelitis
- Native joint
- Prosthetic joint
- Urinary tract
- Other

The following enrollment categories (as determined by DRC unless otherwise stated) will be used for the analysis.

- Refractory

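### As written, a step-down subject who is asymptomatic at baseline and stops ibrexafungerp after very little drug can be scored a Complete Response in the primary ITT analysis

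*SAP*

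**What the plan says.** - **Time point.** SAP 7.1.1 analyses VVC, CMC, CPA and ABPA at TOC, "and at EOT for all other diseases". SAP Table 1 places EOT at the last dose, with an upper limit of 180 days and no lower limit.
- **Early stopping.** Protocol 11.3 says for non-VVC diseases that "at the time of discontinuation, all EOT procedures should be performed for subjects who discontinue from treatment on or before the EOT visit".
- **Success rule.** The Complete Response row of SAP Table 6 (same text in protocol Table 17) has a separate line for subjects enrolled for step-down therapy and asymptomatic at baseline: "no new symptoms or signs suggestive of disease and no new positive cultures". The footnote adds that "DRC adjudications followed this definition for all subjects".
- **Population.** SAP 7 states: "The ITT analyses will be considered primary". SAP 3.2 defines ITT as "all subjects who are enrolled in the study and receive at least 1 dose of study drug".
- **Sufficient exposure.** Only the supportive Per-Protocol set requires that a subject "received enough study drug (ibrexafungerp) to enable clinical efficacy judgement as determined by the DRC".
- **Not Evaluable.** Table 6 describes this category as one for missing data.

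**The concern.** Ordinary subjects have to earn success under Table 6. They must show resolution or improvement, and little or no improvement is a Stable Response, which counts as Failure. A step-down subject without symptoms at baseline starts in a state that already meets the success criterion and can only lose it. Because EOT follows the last dose, stopping early shortens the time in which anything new could appear. A subject who stops for intolerance after a dose or two, and returns to other treatment, may therefore count as a success that the earlier therapy produced.

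The study has no control arm in which such an artefact would cancel, and protocol 18.4.3 has the response rates assessed against external data. Step-down cases enter two enrollment rows in SAP 7.1.1 (their own, and the resistance row that includes them), as well as the disease-level and overall rates.

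The plan uses the missing conditions elsewhere. VVC success in SAP Table 5 rules out additional antifungal use. The acute invasive candidiasis/candidemia completion endpoint in SAP Table 7 rules out both other antifungals and discontinuation. PP requires enough drug. None of these reaches this line of the primary ITT endpoint.

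**Working it through.** **Tracing one case.** Take a subject with acute invasive candidiasis, enrolled for step-down and asymptomatic at baseline, who is dosed on Day 1 only, stops for intolerance and is examined at that point.

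| Step | Rule | Result |
|---|---|---|
| In ITT? | SAP 3.2: one dose | Yes |
| Primary time point | SAP 7.1.1, SAP Table 1, protocol 11.3 | EOT, assessed at stopping |
| Data missing? | SAP Table 6, Not Evaluable | No, the subject was assessed |
| Anything new? | SAP Table 6, step-down line | No |
| Category | SAP Table 6 | Complete Response, in the numerator |
| In PP? | SAP 3.2, DRC judgement on drug received | May be excluded |

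No step asks how much drug was taken or whether another antifungal was started.

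**Plan's own figure.** N = 220 (+10%) has no formula behind it (SAP 3.1), so there is nothing to reproduce. The documents give no count of step-down subjects, of those asymptomatic at baseline, or of early stops. The sizes below rest on assumptions.

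**Per subject, overall.** Compared with failure coding, each such subject adds 1/220 = 0.45 percentage points.

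**Overall range (assumed).** Let 10–30% of subjects be asymptomatic step-down cases, of whom 5–15% stop early with nothing new.
- Low: 220 × 0.10 × 0.05 = 1.1 subjects; 1.1/220 = 0.5 points.
- High: 220 × 0.30 × 0.15 = 9.9 subjects; 9.9/220 = 4.5 points. This needs both maxima at once.

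**Effect on the interval (illustrative).** The only response rate in the documents is the preliminary review in protocol 7.1: 11/20 = 55%. Applied to 220, that is 121 successes, Clopper-Pearson 95% CI 48.2–61.7%. Moving k such subjects out of the successes gives:

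| k | Coded as failure | 95% CI | Excluded instead |
|---|---|---|---|
| 2 | 119/220 = 54.1% | 47.3–60.8% | 119/218 = 54.6% |
| 4 | 117/220 = 53.2% | 46.4–59.9% | 117/216 = 54.2% |
| 11 | 110/220 = 50.0% | 43.2–56.8% | 110/209 = 52.6% |

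**Step-down row.** The shift in points is 100 × a × s. Here a is the share of the row that was asymptomatic at baseline, and s is the share of those who stop early with nothing new. With s = 5–15% (assumed), a = 0.5 gives 2.5–7.5 points, and a = 1 gives the ceiling of 5–15 points. For an assumed row of 20 with 16 successes (80%, CI 56.3–94.3%), recoding two gives 14/20 = 70% (45.7–88.1%), and recoding four gives 12/20 = 60% (36.1–80.9%).

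**The case against.** A reader might infer that every such subject *is* a Complete Response, that the look closes on the day of stopping, and that the step-down row is inflated by the full early-stop share. The documents do not support that reading.

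- **The endpoint is adjudicated.** Detailed criteria are in a DRC Charter that is not among the documents. SAP Table 5 (footnote e) and the note under protocol Table 17 let the DRC use its judgement when the consensus criteria do not fully fit. The last sentence of SAP 7.1.1 sends outcomes called neither success nor failure to not evaluable, without naming missing data. What remains of the concern is that a specific written rule does fit this case, that the SAP says the DRC followed it, and that SAP 3.3 and protocol 18.4.3 tie the unknown category to missing data.
- **Later cultures count.** Under SAP 7.2.3 a positive culture before the FU visit makes the primary result non-successful, and protocol 11.3 asks for the 6-week visit after early discontinuation. This is a partial safeguard. Protocol 14.2.2.3 does not make follow-up cultures mandatory outside bloodstream infection, and a subject back on effective therapy may have no positive culture to find. For bloodstream infection the same section requires two consecutive negative blood cultures, but it does not say whether cultures taken before entry qualify.
- **Other outputs would show it.** PP, the separate step-down row, Global Response at Day 42 and 6-week FU, and the completion endpoint for acute invasive candidiasis/candidemia would all help a reader see the problem. None of them changes the primary figure.
- **The row is mixed.** It holds all subjects the investigator assigned to step-down, while the rule covers only those asymptomatic at baseline. The share a therefore cannot be taken as 1.
- **Timing.** SAP 1.1 (April 2024) describes the adjudications in the past tense. Redefining success after open-label adjudication would itself be a post hoc change to the primary endpoint. This argues for an added analysis over a forced rewrite.

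**Conclusion.** The point holds as a statement about the text. Under SAP Table 6 and protocol Table 17, an asymptomatic step-down subject with very little exposure, an EOT assessment and no new finding can count as a primary ITT success. A stated rule produces this; it is more than an omitted detail. The rule does not cover VVC, CPA or ABPA, subjects who stop with new signs, or subjects with no EOT assessment.

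The size is unknown. The firm figure is 0.45 points per subject on N = 220. The 0.5–4.5 point overall range is assumption only, and the step-down effect is the early-stop share times an unknown share asymptomatic at baseline. The overall effect may well be small; the step-down effect need not be.

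A reader might also conclude that the primary analysis is invalid or that its definition has to be replaced. The documents do not support that: the study is exploratory, supportive analyses exist, the frequency is undocumented and DRC adjudication may already be complete. This is a should-fix point.

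**What to change.** In SAP 7.1.1, before database lock, add an ITT analysis of Global Response (overall, by disease and for the step-down row). It counts as non-success any subject who qualifies only under footnote a of Table 6 and who meets either condition:

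1. the DRC judged that the subject had not received enough ibrexafungerp for an efficacy judgement (the existing PP criterion); or
2. the subject switched to another systemic antifungal at or before the EOT assessment. An approved combination partner is not a switch.

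Report the number of such subjects, show asymptomatic step-down subjects separately, and place this rate beside the primary one wherever results are compared with external data. If adjudication is not final, the same condition can instead be added to footnote a in both SAP Table 6 and protocol Table 17, with the DRC Charter aligned.

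The cost is one more table, one programmed condition that reuses a DRC judgement and concomitant-medication data already collected, and a somewhat lower response rate in that table. It changes scoring only, not the treatment of any subject.

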13.2 Prohibited Medications

Medications not permitted include the following:

- Non-study systemic or topical antifungal therapy except in subject subgroups where combination therapy is allowed or where an exception was granted by the Sponsor on a per-subject basis
- Other investigational drug(s)
- Strong CYP3A4/5 inhibitors, CYP3A4/5 inducers, and select P-gp substrates (refer to Appendix B [[Section 21.2](#)] for the full list of prohibited medications).

See Appendix B [[Section 21.2](#)] for the full list of prohibited medications

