**Table 5 Efficacy Time Points and Outcome Definitions for Primary and Secondary Endpoints**

Fungal disease	Primary time point (Secondary time points)	Primary Outcome Definition	Secondary Outcome Definitions (disease-specific outcome definitions, if not previously defined) a, e
Acute or chronic invasive candidiasis, including candidemia	EOT (EOT, Day 42, 6-Week FU)	Global Response = Global Response based on MSG-EORTC outcome response definitions b	Global Response (as defined) Clinical Response (including radiological outcome) and Mycological Response Clinical and Mycological Responses based on MSG-EORTC outcome response definitions b
Acute or chronic severe mucocutaneous candidiasis, including: 
 
• Esophageal candidiasis (EC)
 
• Oropharyngeal candidiasis (OPC)
 
• Chronic mucocutaneous candidiasis (CMC)
 
• Vulvovaginal candidiasis (VVC)
 
	For EC and OPC : EOT (EOT, Day 42, 6-Week FU)	For EC and OPC: Global Response = Global Response based on MSG-EORTC outcome response definitions b	For EC and OPC: Global Response (as defined) Clinical Response (including radiological outcome) if done as SOC and Mycological Response Clinical and Mycological Responses based on MSG-EORTC outcome response definitions b
	For CMC: TOC (Day 84) or EOT, whichever occurs first (EOT, Day 42, Day 84, 6-Week FU)	For CMC: Global Response = Global Response based on MSG-EORTC outcome response definitions b	For CMC: Global Response (as defined) Clinical Response (including radiological outcome) and Mycological Response Clinical and Mycological Responses based on MSG-EORTC outcome response definitions b

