	For VVC: TOC (Day 17) (Day 17, 25-Day FU [Day 32], 35-Day FU [Day 42])	For VVC: Global Response = Clinical Success , defined as at least 50% reduction from baseline in total composite score, without use of additional antifungal	For VVC: Global Response (as defined) Clinical Response : 
 
• Clinical Cure, defined as complete resolution of all signs and symptoms (VSS = 0) without use of additional antifungal (Reference FDA guidelines 2016); OR
 
• Resolved VVC infection (VSS < 3)
 
 Mycological Response : 
 
• = mycological eradication of the baseline pathogen OR
 
• Presumed eradication of the baseline pathogen Symptom resolution at FU (clinical cure, resolved infection, clinical success)
 
 Responder outcome (clinical cure and mycological eradication)

Fungal disease	Primary time point (Secondary time points)	Primary Outcome Definition	Secondary Outcome Definitions (disease-specific outcome definitions, if not previously defined) a, e
Disseminated/invasive dimorphic fungi: 
 
• Coccidioidomycosis
 
• Histoplasmosis
 
• Blastomycosis
 
	EOT (EOT, Day 42, Day 84, 6-Week FU)	Global Response = Global Response based on MSG-EORTC outcome response definitions b	Global Response (as defined) Clinical Response (including radiological outcome) and Mycological Response Clinical and Mycological Responses based on MSG-EORTC outcome response definitions b

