**Table 7      Disease-Specific Secondary Endpoints**

Disease-Specific Secondary Endpoints	
Acute Invasive candidiasis / Candidemia	

○ Completion of study drug antifungal treatment (i.e. no recurrence, no use of other antifungal treatment, no discontinuation for any reason)

	
Chronic Severe Mucocutaneous Candidiasis (CMC)	

○ Percentage subjects with mycological cure at Day 84

○ Percentage subjects with clinical response by Day 42 and Day 84

○ Percentage of subjects with continued symptom relief at 6-week FU

	
Chronic Pulmonary Aspergillosis (CPA) disease-specific endpoints	

○ Six-Minute Walk Test and MRC Dyspnea Score at Day 90 and Day 180

○ Weight change at Day 90 and Day 180

○ Improvement in inflammatory markers (CRP, plasma viscosity, albumin, platelet count, disease-specific immunoglobulin levels) at Day 90 and Day 180

○ Change in total IgG and Aspergillus IgG at Day 90 and Day 180, if elevated at Baseline

○ All-cause mortality at Day 90, Day 120 and Day 180

○ Recurrence at Day 180

	
Allergic Bronchopulmonary Aspergillosis (ABPA) disease-specific endpoints:	

○ Percentage of subjects who exhibit a Global Response at Day 42

○ Percentage of subjects with Clinical Improvement (as measured on a 4-point scale) at TOC, Day 90, Day 180, then every 3 months while on therapy, and 6-Month FU

○ Percent decline in total IgE (baseline IgE minus time point IgE/baseline IgE) at Day 42 and Day 90

○ Number of subjects who experience an ABPA exacerbation at the 3-Month and 6-Month FUs

○ Time to first ABPA exacerbation

○ Change in lung function (FEV1 and FVC) at Day 42

○ Number of Asthma exacerbations and ABPA exacerbations at the 3-Month and 6-Month FUs

○ All-cause mortality at Day 90, Day 120 and Day 180

	
Invasive Pulmonary Aspergillosis (IPA) disease-specific endpoint	

- The percentage of subjects who attain a GMI decrease including absolute and percent reduction from Baseline to Weeks 1, 2, 4 and 6, when feasible
- Time to achieve a clinically meaningful GMI absolute (<0.5) and percent (=>50%) decrease
- All-cause mortality at Day 84

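### Outside VVC, no response definition scores the use of another antifungal, so improvement on a replacement drug can count as an ibrexafungerp response, mainly at the follow-up time points

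*SAP*

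**What the plan says.** For VVC, SAP Table 5 makes Global Response conditional on the subject not having needed another drug: it is "defined as at least 50% reduction from baseline in total composite score, without use of additional antifungal". VVC clinical cure carries the same condition.

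For the diseases scored by the EORTC-MSG criteria, SAP Table 6 (Protocol Table 17) governs. Complete Response requires survival and "resolution of all attributable symptoms and signs of disease and radiological abnormalities, and mycological evidence of eradication of disease". Partial Response requires survival, the absence of fresh positive cultures, and "improvement in attributable symptoms and signs of disease and radiological abnormalities, and evidence of clearance of cultures or reduction of fungal burden". The failure rows are stable response, death and "Progression of Fungal Disease: Evidence of progressive fungal disease based on a composite of clinical, radiological and mycological criteria". The CPA and ABPA rows of Table 5 have their own criteria. None of these mentions other antifungals.

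Table 5 applies the definitions after treatment as well as at EOT. For invasive candidiasis, EC and OPC the time points are "EOT, Day 42, 6-Week FU". CMC, dimorphic fungi, IPA and other emerging fungi add Day 84. CPA and ABPA use Day 90 and Day 180.

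Protocol 11.3 lists worsening or slow response that calls for a different treatment as a reason to stop. It then states: "All follow up visits should be completed for discontinued subjects regardless of need for additional antifungal therapy". Protocol 13.2 prohibits other antifungals except where combination therapy is allowed or "where an exception was granted by the Sponsor on a per-subject basis".

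**The concern.** This is a single-arm study, and Protocol 18.4.3 says its response rates will be set against external data. A response produced by a second drug and credited to ibrexafungerp raises the rate, and no control arm absorbs the error.

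The plan anticipates the event (stopping for alternative therapy, with visits continuing) but gives it no response category in ITT. It also shows awareness of the issue elsewhere. VVC Global Response penalises additional antifungals, and the acute invasive candidiasis/candidemia completion endpoint in SAP Table 7 requires "no recurrence, no use of other antifungal treatment, no discontinuation for any reason". The overall rate across disease categories therefore pools one definition that penalises rescue with others that are silent on it.

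**Working it through.** No stated figure bears on this point; the planned 220 subjects come without a calculation. The check is mainly textual.

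**1. Is there a condition on other antifungal use?**

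| Definition | Condition? |
|---|---|
| VVC Global Response and clinical cure (SAP Table 5) | Yes |
| Complete and Partial Response (SAP Table 6) | No |
| Failure rows (SAP Table 6) | Not listed as failure |
| CPA and ABPA responses (SAP Table 5) | No |
| Investigator's scales (SAP 7.2.3) | No |
| Acute IC/candidemia completion (SAP Table 7) | Yes, but a separate secondary endpoint |

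**2. Does another rule catch these subjects?**

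- SAP 7 excludes from PP any unapproved co-administered antifungal given for at least 10% of treatment or more than 3 days, whichever is shorter. The threshold is min(0.10 × days treated, 3): 0.7 day for a 7-day course, and 3 days for courses of 30 days or more. It does not touch ITT. On its wording it also misses a replacement started after the last ibrexafungerp dose, which is not co-administration.
- SAP 7 also excludes from PP a non-VVC EOT visit more than 2 weeks after the last dose. That visit stays in ITT.
- SAP 7.2.3 assigns mycological failure for recurrent or emergent infection, but only after an earlier mycological success followed by positive cultures. Recurrence (Protocol 18.4.2.2) requires a Global Response at EOT. Neither covers a non-responder who is switched and then improves.
- No rule carries a failure at EOT forward to later visits.

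**3. Which time points are exposed?**

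Protocol Table 3 sets EOT at the last dose, and Protocol Table 14 gives a window of ±3 days. Time off drug at a later visit is visit day minus days treated. Protocol 7.1 reports 7 to 90 days of treatment, mean about 37, in the first 20 subjects.

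- Treated 7 days: 42 − 7 = 35 days off drug at Day 42, and 84 − 7 = 77 at Day 84.
- Treated 37 days: 42 − 37 = 5 days at Day 42, and 84 − 37 = 47 at Day 84.
- 6-Week FU: about 42 days for every subject.

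The conditions named for those 20 subjects have no Day 84 response in Table 5, so the Day 84 figures only illustrate the interval.

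At the primary time point the routes are narrower: antifungals added during treatment; late EOT visits kept in ITT; and, for CMC, CPA and ABPA, the SAP 7.1.1 rule that uses a later EOT response when Day 84 or Day 90 is not evaluable or not done.

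**4. Illustration of size (shares assumed)**

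The preliminary review found 11/20 = 55.0% success. Applied to 220 subjects this is 121 successes. Let k successes have used an antifungal that would be reclassified. The rate becomes (121 − k)/220, with Clopper-Pearson 95% intervals as in the SAP:

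| Assumed share of ITT | k | Rate | 95% CI |
|---|---|---|---|
| 0% | 0 | 55.0% | 48.2–61.7 |
| 2% | 4 | 53.2% | 46.4–59.9 |
| 5% | 11 | 50.0% | 43.2–56.8 |
| 10% | 22 | 45.0% | 38.3–51.8 |

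The interval half-width at 55.0% is about 6.8 points. The denominator of 220 includes any VVC subjects, whose Global Response already has the condition.

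**The case against.** A reader might infer that the primary EOT rate is inflated wholesale by rescue cures. The documents do not support that. Protocol 11.3 calls for EOT procedures at the time of discontinuation, and for CMC, CPA and ABPA an early EOT becomes the TOC. A subject switched for poor response is therefore normally scored at the switch, and Table 6 classes minor or no improvement, or progression, as failure. This objection stands and limits the point mainly to follow-up time points.

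The SAP does address unapproved co-administration and late EOT visits, and PP is a named supportive analysis. Protocol 18.4.3 also promises results by receipt of combination therapy, although SAP 7.1.1 does not list that breakdown. These measures help, but they leave ITT unchanged and do not reach replacement therapy begun after the last dose.

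The primary endpoint is DRC-adjudicated. The Charter holds further criteria, and a note to SAP Table 5 lets the DRC use its own judgement where the consensus criteria do not fully apply. A rule may therefore exist. What is shown is its absence from the protocol and SAP, not that the DRC scored rescued subjects as successes.

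Finally, being off ibrexafungerp at Day 42 does not imply rescue, since completed courses also end. Approved combination therapy is part of the design, so failing every later addition would be a debatable choice.

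**Conclusion.** The gap is real and should be fixed. Outside VVC, neither document scores use of another antifungal for the baseline infection in ITT. A subject who stops for poor response and improves on a replacement can meet Global, Clinical or Mycological Response at Day 42 and the 6-Week FU; at Day 84 for CMC, dimorphic fungi, IPA and other emerging fungi; and at Day 90 or Day 180 for CPA and ABPA. For subjects who stopped before the earlier of these visits, this assumes that the visit is made and assessed. The 6-Week FU is explicitly required after discontinuation.

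Exposure at the primary time point is limited to the three routes under step 3 of the working. The size cannot be computed: the documents give no rate of other-antifungal use, and the table above only shows what assumed shares of 2% to 10% would do. The conclusion would soften to a request to restate the rule in the SAP if the Charter already contains one.

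**What to change.** In SAP 7.1.1 and 7.2:

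- Keep the DRC-adjudicated rate as the primary result at EOT/TOC.
- Add a pre-specified ITT analysis for all non-VVC diseases. A subject who, before the assessed time point, received an antifungal for the baseline infection outside the planned or Sponsor-approved combination regimen is a non-success at that time point and later ones, for Global, Clinical and Mycological Response.
- Make this the reported rate for post-EOT time points.
- Show subjects with Sponsor-approved later additions separately.
- Report the number reclassified by disease and time point.
- If the DRC Charter already has a rule, state it in the SAP.

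The change concerns scoring only. Protocol 13.1 and SAP 6.1 already record antifungal use through the last observation, so the work is a derivation plus a check of indication and approval status for each affected subject. SAP Table 6 describes DRC adjudications in the past tense, which is a further reason to add an analysis and leave the adjudicated endpoint as it is. If the database is already locked, the analysis should be labelled post hoc. The downside is slightly lower rates, and subjects switched for logistic or tolerability reasons count as non-success in that analysis.
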